Study Design

This is a single arm, open label, prospective study evaluating the safety and clinical efficacy of the combination of nivolumab, ipilimumab and hypofractionated palliative radiation therapy (SBRT) in patients with advanced salivary gland cancer.

Patients enrolled will receive the following treatment (see Section 5.1.1):

1. Nivolumab 3mg/kg IV Q 2 weeks x 12 doses followed by Nivolumab 480 mg IV Q4 weeks x 8 doses
2. Ipilimumab 1 mg/kg IV Q6 weeks x 4 doses
3. Hypofractionated radiation therapy (SBRT) given to a total dose of 24Gy given in 3 fractions every other day over 1 week and initiated 2 weeks after the first dose of nivolumab and ipilimumab. The target lesion will be a local/regional or metastatic disease site that per the multidisciplinary head and neck team, requires local control for palliation and/or prevention of impending symptoms.

Both nivolumab and ipilimumab have well established toxicity profiles as a single agent and in combination. However, since the combination of nivolumab, ipilimumab and palliative radiation has not previously been described or studied, the first 6 patients who will be enrolled in this study will represent the initial safety run-in phase. Patients will receive full dose nivolumab and ipilimumab. Enrollment will be halted until these first 6 patients complete the first 12 weeks of treatment and acute toxicities will be reviewed. If more than 2 DLTs (to be defined in Section 5.1.2) are noted in this 6 patient cohort, a dose modification will be implemented (Section 5.1.1) for the remaining 14 patients who will be enrolled in the expansion cohort. Enrollment period is 24 months and duration of the trial 48 months.

Study Population

The study aims to enroll patients with salivary gland carcinomas (WHO, 2005), who are not candidates for curative intent therapy and who have a target lesion (either local/regional or distant metastatic site involving the lung and/or bone), that requires local control for palliation, as determined by a multidisciplinary team.

Inclusion Criteria:

1. Histologically proven salivary gland carcinoma (WHO, 2005) arising from a previous head and neck primary site, and located within the head and neck region, lung or bone, and who are not candidates for curative intent therapy.
2. ≥ 18 years old at the time of signing informed consent.

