4. INVESTIGATIONAL PLAN/STUDY DESIGN

4.1 Study Design Overview

This study will be carried out as a single institution, single arm phase I/II unblinded trial. A maximum of 20 patients will be enrolled. Each patient will be treated with nivolumab, ipilimumab and stereotactic body radiation therapy. Nivolumab will be continued for a total of 12 cycles, unless evidence of unacceptable toxicity, disease progression or withdrawal of patient consent were to occur.

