5.1.3.1 Dose Delay Criteria

Doses of both nivolumab and ipilimumab (during study weeks 1-24) or nivolumab alone (during study weeks 25-52) should be held if any of the following are observed:

- Any Grade ≥ 3 non-skin, drug-related adverse event, except for fatigue and laboratory abnormalities

- Any Grade ≥ 3 drug-related laboratory abnormality with the following exceptions for lymphopenia, aspartate aminotransferase (AST), alanine aminotransferase (ALT), or total bilirubin or asymptomatic amylase or lipase:
 - Grade 3 lymphopenia does not require a dose delay
 - If a subject has a baseline AST, ALT, or total bilirubin that is within normal limits, delay dosing for drug-related Grade 2 toxicity
 - If a subject has baseline AST, ALT, or total bilirubin within the Grade 1 toxicity range, delay dosing for drug-related Grade ≥ 3 toxicity
 - Any Grade ≥ 3 drug-related amylase or lipase abnormality that is not associated with symptoms or clinical manifestations of pancreatitis does not require dose delay.
- Any AE, laboratory abnormality or inter-current illness which, in the judgment of the investigator, warrants delaying the dose of study medication.

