8.4 STUDY STOPPING RULE

In keeping with the study primary endpoint, a stopping rule will be implemented in the unlikely event that the combination under study is deemed to have unacceptably high toxicities. Enrollment will be halted if more than 3 patients experience a Grade 4 or higher drug related toxicity (CTCAE v. 5) during the trial treatment period or up to 30 days after the last investigational drug infusion. The likelihood of observing more than 3 Grade 4+ drug-related adverse events is 80% if the true

rate is 20% and the likelihood is 91% if the true rate is 25%. This rule has an 83% chance of prematurely discontinuing trial enrollment after the 1st 10 patients are enrolled if the true rate of Grade 4 drug related toxicity is 40%. The study will be reviewed by the University of Washington/Fred Hutch Cancer Consortium Data and Safety Monitoring Committee (DSMC

STATISTICAL CONSIDERATIONS

All patients enrolled in the study, including those in the run-in phase will be included in the analysis of toxicity and efficacy.

Safety and tolerability is the primary endpoint of this study, and all patients enrolled will be assessed for this endpoint. Adverse events will be recorded and graded based on CTCAE v. 5, and their relationship to the experimental agents reported.

Similarly, all patients enrolled in the study (i.e., the initial 6 patient cohort, and the additional 14 patient expansion) will be included in the efficacy analyses. Clinical responses to the combination of nivolumab, ipilimumab and hypofractionated radiation will be based on RECIST 1.1 criteria. Oncologic outcome endpoints such as progression free and overall survival will be calculated from the date of study enrollment, until disease progression or death from any cause, respectively. Survival estimates will be calculated using the Kaplan-Meier method.

Exploratory endpoints of this study include correlative work performed on research serum and tissue samples.

Sample size determination

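### The 83% early-halt probability in Section 8.4 assumes all ten outcomes are known before patient 11 enters, which the counting window and accrual plan do not provide

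*Combined protocol and SAP*

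**What the plan says.** Section 8.4 (Study Stopping Rule) sets the rule: "Enrollment will be halted if more than 3 patients experience a Grade 4 or higher drug related toxicity". The counting window is "during the trial treatment period or up to 30 days after the last investigational drug infusion". Sections 5.1.1 and 5.1.3.1 run treatment to week 52.

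Three probabilities follow in Section 8.4:

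- For a true rate of 20%: "The likelihood of observing more than 3 Grade 4+ drug-related adverse events is 80" per cent.
- For a higher rate: "the likelihood is 91% if the true rate is 25" per cent.
- For a true rate of 40%: "This rule has an 83% chance of prematurely discontinuing trial enrollment after the 1st 10 patients are enrolled".

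The first two concern observing events. Only the third is worded as a chance of stopping accrual.

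On size and timing, Section 4.1 says "A maximum of 20 patients will be enrolled", and the Synopsis (Study Design) says "Enrollment period is 24 months and duration of the trial 48 months". The Synopsis and Section 4.2 hold enrolment until the first 6 patients have completed 12 weeks. No later step makes enrolment wait for follow-up. Section 8.4 gives no formula, onset assumption or allowance for incomplete follow-up.

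**The concern.** A binomial tail for ten patients is the chance that enough of them eventually have an event. It equals the chance of stopping at patient 10 only if each outcome is known before patient 11 enters. Here a patient can contribute an event for about 13 months after starting, while patients 7 to 20 enter without waiting.

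Safety is the primary endpoint, and Section 9 asks the review committees to evaluate stopping rules. If they take 83% as the chance that a regimen with a 40% Grade 4 rate is stopped by the tenth patient, they are relying on a property that the design has only if toxicity appears very early. Further patients could be enrolled while events in earlier patients are still to come.

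**Working it through.** **Inputs from the protocol.** Limit: more than 3 patients (8.4). Window: 52 weeks plus 30 days = 364 + 30 = 394 days, about 13 months at most (8.4, 5.1.1). Patients: 20 (4.1). Accrual: 24 months (Synopsis). Hold: 12 weeks after patient 6 (Synopsis, 4.2).

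**Inputs assumed, because the documents give none.** Entry pattern: random or evenly spaced over 24 months including the hold. Onset of toxicity: uniform over 0–1, 0–3, 0–6 or 0–13 months.

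**Step 1: reproduce the stated figures.** Let X be binomial(n, p), with every outcome known.

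For n = 10, p = 0.4:

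- P(X ≥ 3) = 1 − [0.6^10 + 10(0.4)(0.6^9) + 45(0.4²)(0.6^8)] = 1 − [0.0060 + 0.0403 + 0.1209] = 0.833.
- P(X ≥ 4) = 0.833 − 120(0.4³)(0.6^7) = 0.833 − 0.215 = 0.618.

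| n, true rate | Stated | 3 or more | More than 3 (as written) |
|---|---|---|---|
| 20, 20% | 80% | 79.4% | 58.9% |
| 20, 25% | 91% | 90.9% | 77.5% |
| 10, 40% | 83% | 83.3% | 61.8% |

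The stated figures are complete-follow-up binomials at a limit one lower than the written rule. The rule and its figures have to be reconciled in any case; both limits are carried below.

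**Step 2: direction.** For any fixed limit, the events known when patient 11 arrives are a subset of the eventual events in patients 1 to 10. Hence P(halt before patient 11) ≤ P(X ≥ limit). No onset assumption is needed.

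**Step 3: follow-up at patient 11.** Take even spacing. The hold is 84 days, or 2.76 months, leaving 24 − 2.76 = 21.24 months for 19 gaps of 1.118 months each. Patient 11 enters at 10 × 1.118 + 2.76 = 13.94 months. Patient 1 has then been followed for 13.94 months and patient 2 for 12.82, just short of the full window (394 / 30.44 = 12.94 months). So 9 of the first 10 would still be inside a full window. Patients 7 to 10 would have only 1.1 to 4.5 months.

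**Step 4: size.** Simulated probability of halting before patient 11 at a true rate of 40%. Ranges span random and even entry:

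| Onset uniform over | 3 or more | More than 3 |
|---|---|---|
| No delay | 83.3% | 61.8% |
| 0–1 month | 80–83% | 57–62% |
| 0–3 months | 73–77% | 47–52% |
| 0–6 months | 63–65% | 36–38% |
| 0–13 months | 38–41% | 15–17% |

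These are approximate; spacing and the placing of the hold move them by a few points. A separate even-entry run with onset over 12, 24 and 56 weeks gave 78.5%, 69% and 41% at 3 or more, and 55%, 42% and 17% at more than 3. In that run, mean enrolment rose from 7.5 with no delay to between 8.1 and 11.8 at 3 or more, and from 10.0 to between 10.6 and 14.3 at more than 3.

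**Step 5: the 20-patient figures.** Halting before patient 20 can use only 19 patients, so the no-delay value is binomial with n = 19. At 3 or more and a rate of 20%: 1 − [0.8^19 + 19(0.2)(0.8^18) + 171(0.2²)(0.8^17)] = 1 − [0.0144 + 0.0685 + 0.1540] = 76.3%. At 25% it is 88.9%. With random entry and onset over 0–3, 0–6 or 0–13 months these become 71%, 65%, 49% and 85%, 80%, 65%. At a 40% rate, over both limits and all these onset patterns, the rule still halts before patient 20 in about 80–99% of runs.

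**The case against.** A reader might infer that all three probabilities are inflated by delay, so that the rule stops less often than claimed at any threshold. The documents do not support that. The 80% and 91% are worded as likelihoods of observing events; as final counts over 20 patients, delay leaves them unchanged. Setting them against the chance of halting before patient 20 also mixes two effects, because part of the gap comes from dropping patient 20 (79.4% to 76.3%, and 90.9% to 88.9%).

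The 83% can itself be read more loosely, as the first ten patients' events halting accrual at some point before it closes. On that reading, with a limit of 3 or more, the figure stays at about 83% under 24-month accrual. That reading gives up the assurance of an early halt, which is what the sentence appears to offer.

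The size is driven by assumptions, and the 13-month case is the least supported. It needs patients to stay on treatment for the full year with onset spread evenly to the end. Radiation is given in week 3, ipilimumab falls within weeks 1–24, and the Introduction cites a median progression-free survival of 5–6 months in two earlier chemotherapy studies. If onset is within a month, the loss is at most about 3 points at 3 or more.

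Other safeguards exist. The first 6 patients are watched for 12 weeks, and Section 5.1.1 changes the regimen for the remaining 14 after 2 or more DLTs (the Synopsis and Section 4.2 say more than 2). Staff review adverse events weekly (Section 3). A constant 40% rate in all 20 patients ignores the regimen change. A reader might also infer that reaching the limit after enrolment closes escapes review, but Section 9 covers studies still treating patients.

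Finally, complete-follow-up binomials are a common shorthand in small single-arm studies. That is acceptable if they are labelled as such; here the 83% is presented as the chance of halting enrolment.

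**Conclusion.** The point holds for the 83%. As worded, it describes when accrual stops, yet it is calculated as though all ten outcomes were known. At any fixed limit the true chance of halting before patient 11 cannot exceed the complete-follow-up value (83.3% at 3 or more, 61.8% at more than 3) and will usually be lower. The shortfall runs from almost nothing with onset inside one month to about 45 points with onset spread over 13 months (83% against 38% or more, at 3 or more). It depends on the assumed onset and entry patterns and on a constant 40% rate.

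At that rate the consequence is mainly later halting, with more patients enrolled, rather than failure to halt. The 80% and 91% need a correct label: they are not probabilities of halting enrolment. The mismatch between the written limit and all three figures is a separate error that needs no assumption. Correcting it alone would leave another complete-follow-up figure (61.8%) presented as a chance of halting.

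**What to change.** When the limit and its figures are reconciled, rewrite the same paragraph of Section 8.4:

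1. Label the 20-patient figures as the probability that the limit is ever reached among 20 fully followed patients.
2. Replace the 83%, or state that it is conditional on complete follow-up of the first 10. Beside it, give simulated probabilities of halting before patient 11 and before patient 20, with the mean number enrolled.
3. Run the simulation with 24-month accrual, the 12-week hold after patient 6, and two or three stated onset patterns, at true rates of 20%, 25% and 40%.

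The cost is a short simulation, one rewritten paragraph and a less favourable stated figure. It needs no extra patients and no change to the clinical rule.

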4.2 Study Schema

Note: refer to Dosing and Administration (Section 5.1.1) for further details on treatment scenarios.

Clinical Study Protocol RG1718030
Drug Substance: Nivolumab and Ipilimumab
IND Number:140818
Protocol version 3.0 April 17, 2019

Both ipilimumab and nivolumab are FDA approved, and the safety profile of both agents have been extensively studied. However, because the combination with radiation has not been previously studied, the first 6 patients of this study will represent the initial run-in phase of the triplet combination of nivolumab, ipilimumab and palliative radiation. The initial doses of ipilimumab and nivolumab will be administered on day 1 of therapy.

Stereotactic radiation will be initiated on Week 3 of treatment. SBRT will be delivered to a total dose of 24 Gy, given in 3 fractions of 8Gy every other day. Treatment will be continued according to the study schema unless patient withdraws consent, has confirmed disease progression, and/or develops toxicity that results in treatment discontinuation.

Enrollment will be halted until these first 6 patients complete the first 12 weeks of treatment and acute toxicities will be reviewed. If more than 2 DLTs (to be defined in Section 5.1.2) are noted in this six patient cohort, a dose modification will be implemented (Section 5.1.1) for the remaining 14 patients who will be enrolled in the expansion cohort.

Serum correlative studies will be collected at the following timepoints: at baseline, prior to week 8, and prior to week 16 of treatment. Archived formalin fixed paraffin embedded tissue (obtained in the 12 months prior to trial enrollment) will be collected from patients enrolled. If the patient does not have archived tissue available, a fresh biopsy will be obtained. Tissue requirement will be waived if deemed contraindicated or not clinically available/accessible for resection per the treating physician (PI approval required).

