There are multiple ongoing studies in various tumor types exploring the activity of nivolumab and ipilimumab. In a published report of the combination in patients with advanced NSCLC treated on a phase I study (Checkmate, 012), treatment related serious adverse events were observed in 28% of patients (Hellmann Lancet Oncol 2017). This study plans to accrue 20 patients, a sample size that would allow us to estimate grade 3 or higher acute drug related toxicity rate of 30% with a confidence interval of 20% (95% confidence level) or an upper bound of 50%. This would allow us to reasonably exclude a clinically significant increase in toxicity with the addition of radiation therapy to the nivolumab and ipilimumab combination as defined by the upper bound of the confidence interval.

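### The primary toxicity rate is taken over all enrolled patients, so any patient enrolled but never dosed would bias the rate and its upper confidence bound downward

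*Combined protocol and SAP*

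**What the plan says.** The Statistical Considerations (printed after Section 8.4) set the analysis population twice. First: "All patients enrolled in the study, including those in the run-in phase will be included in the analysis of toxicity and efficacy". Then, for the primary endpoint: "Safety and tolerability is the primary endpoint of this study, and all patients enrolled will be assessed for this endpoint". The synopsis (Statistical Plan) reports toxicities as counts and percentages of patients.

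Under Sample size determination, "This study plans to accrue 20 patients", and Section 4.1 makes that figure a ceiling: "A maximum of 20 patients will be enrolled". The quantity to be estimated is a "grade 3 or higher acute drug related toxicity rate of 30" per cent, "with a confidence interval of 20% (95% confidence level) or an upper bound of 50" per cent. The plan then says that a material rise in toxicity from adding radiation could reasonably be excluded, "as defined by the upper bound of the confidence interval".

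Three other places bear on who can have an event:

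- Section 8.2 defines an adverse event as arising in a participant who has been given study drug.
- Section 4.1 expects every patient to receive both drugs and SBRT, but gives no rule for a patient who does not.
- Section 4.2 places radiation after the first drug doses: "Stereotactic radiation will be initiated on Week 3 of treatment".

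Nowhere is a treated or safety population defined, and nowhere is enrolment defined as receipt of a first dose.

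**The concern.** A drug-related event can occur only in someone who received drug. A patient enrolled but never dosed therefore cannot enter the numerator, yet under the stated rule stays in the denominator. For an efficacy rate, that kind of dilution is usually cautious. For a toxicity rate it runs the other way and makes the regimen look safer. With about 20 patients, each one carries about 5 percentage points of denominator weight, and the plan draws its safety inference from the upper confidence bound, so the choice of set could show in the reported result.

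A second, smaller issue concerns the triplet. A patient who stops before Week 3 contributes to a rate offered as evidence on drugs plus radiation without having received radiation.

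**Working it through.** **Inputs.** N = 20, a rate of 30%, 95% confidence and an upper bound of 50% (Sample size determination). All enrolled as denominator (Statistical Considerations). Assumption: of 20 enrolled, u = 0 to 3 are never dosed. The documents give no figure for u.

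**1. Reproduce the plan's figure.** The Wald interval is p ± 1.96 × √(p(1 − p)/n). With p = 0.30 and n = 20, the half-width is 1.96 × √(0.21/20) = 0.2008 and the interval is 0.099 to 0.501. This matches the stated 20 points and 50%. At 6/20 the two-sided exact upper limit is 54.3% and Wilson gives 51.9%, so Wald is the closest match, although the plan does not name it.

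**2. Direction of the bias.** With x events among 20 − u dosed patients, the treated rate is x/(20 − u) and the all-enrolled rate is x/20. Their ratio is (20 − u)/20, that is 0.95, 0.90 and 0.85 for u = 1, 2 and 3. The all-enrolled rate is lower whenever u > 0 and x > 0.

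**3. Effect on the upper 95% limit.** Formulas, with z = 1.96:

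- Exact (Clopper-Pearson): the 0.975 quantile of Beta(x + 1, n − x).
- Wilson: [p + z²/(2n) + z√(p(1 − p)/n + z²/(4n²))] / (1 + z²/n).
- Wald: as in step 1, upper end.

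At 5 events:

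| Denominator | Exact | Wilson | Wald |
|---|---|---|---|
| 20 (all enrolled) | 49.1% | 46.9% | 44.0% |
| 19 dosed | 51.2% | 48.8% | 46.1% |
| 18 dosed | 53.5% | 50.9% | 48.5% |
| 17 dosed | 56.0% | 53.1% | 51.1% |

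The number of undosed patients needed to take the limit past 50% is one (exact), two (Wilson) or three (Wald).

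At the plan's own case of 6 events, Wald gives 50.1% for 6/20 and 52.5% for 6/19. That is a one-patient crossing only if 50.1% is rounded to 50%, as the plan does.

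**4. How often the count would fall there.** Assume a true rate of 30% among dosed patients. With one undosed patient, the chance of exactly 5 events in 19 is C(19,5) × 0.3⁵ × 0.7¹⁴ = 0.19. That is the chance of a crossing by the exact method; by Wilson or unrounded Wald it is zero. With three undosed patients, the chance of exactly 5 events in 17 is 0.21, and all three methods then cross.

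**The case against.** A reader might infer that one undosed patient reverses the trial's safety conclusion. The documents do not support that.

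- **Method.** It is true at 5 events with exact limits. The plan names no method, however, and the method that fits its figure, Wald, stays below 50% at 5/19 and 5/18.
- **Status of 50%.** It is the bound expected if 30% is observed. There is no hypothesis test and no rule that the trial succeeds only if the bound falls below it. The stopping rule in Section 8.4 and the run-in rule work on counts, so this denominator does not enter them.
- **Meaning of enrolled.** Section 4.1 expects every patient to be treated, Section 5.1.1 speaks of the later 14 as patients to be treated, and the efficacy paragraph describes the enrolled as the same 6 plus 14. One can read enrolled and treated as interchangeable. If that is meant, the problem disappears, but the plan does not say it.
- **Replacement.** Section 5.1.2 replaces run-in patients who leave early without a dose-limiting toxicity, or who receive under 90% of a day 1 infusion. Those rules serve the dose-limiting toxicity assessment and remove nobody from the all-enrolled analysis.

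A reader might also infer that patients who stop before SBRT should leave the primary rate. They should not. They received drug and can have the drug-related event. If they stopped because of early toxicity, dropping them would itself make the regimen look safer.

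The points on method and on the status of 50% stand and limit the size of the concern. They do not remove it, because the denominator is stated outright and the bias has one direction.

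**Conclusion.** The concern holds as a conditional bias in a stated analysis rule. If any patient is enrolled but never dosed, the all-enrolled denominator understates the grade 3 or higher drug-related rate and its upper limit. For 5 events, each undosed patient lowers the reported upper limit by roughly 2 to 3 percentage points, and it takes one, two or three such patients (exact, Wilson, Wald) for the choice of denominator to decide which side of 50% the limit falls on.

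This rests on two assumptions: that enrolment can precede dosing, and that at least one enrolled patient goes undosed. In a trial of 20 the number may well be zero, and the effect is then nil. The point about patients who stop before radiation supports an additional summary only, not a change to who is in the primary rate.

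**What to change.** In the Statistical Considerations:

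1. Define the primary toxicity set as all patients who received at least one dose of nivolumab or ipilimumab, and say that a partly given infusion counts.
2. List enrolled but undosed patients separately, with reasons.
3. Name the confidence interval method for the primary rate.
4. Add a supportive toxicity rate among patients who also received at least one SBRT fraction. It is reported beside the primary rate and does not replace it.

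Overall and progression-free survival stay on all enrolled patients, as already planned.

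The cost is a few sentences, with no change to treatment, recruitment or data collection. The downside is that the primary denominator may fall slightly below 20 and the interval widen a little.
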